8.1. Data capture

Data capture will be performed using an electronic data collection (EDC) system in conjunction with electronic patient reported outcome (PRO) collection tools implemented in the smartphone application. The clinical sites will use electronic case report forms (eCRFs) to document the information required by the study CIP.

The EDC provider is FlaskData.IO. The EDC enables secure collection, transmission, validation, monitoring and real-time administration of the data collected at the sites and by the smartphone application. The system offers a password-restricted access to clinical trial information based on individuals' roles and responsibilities. The EDC is compliant with 21 CFR Part 11 and FDA's "Guidance: Computerized Systems Used in Clinical Investigations."

Except for patient reported outcomes which are directly reported by the participants in the smartphone application, data reported on the eCRF should be driven from source documents and should be consistent with these source documents. Editing of data will be done with a full audit trail.

PRO data collected from the smartphone application will be saved in dedicated log files on the smartphones for backup purposes and transferred to the EDC system.

8.1.1. Direct data entry

For several CRF fields, source data verification (SDV) may not be possible as entries may not be found in source documents (e.g., migraine diary or other patient reported outcome completed directly into the smartphone app). Therefore, the CRF may be used for direct data entry, but only in pre-defined fields.

8.2. Data quality assurance

To ensure the quality of clinical data across all subjects, a clinical data management review of the patient data in the CRF will be performed by the sponsor. During this review, patient data will be assessed for consistency, omissions, and any apparent discrepancies. In addition, the data will be reviewed for adherence to the CIP and relevant regulations. To resolve any questions arising from the clinical data management review process, data queries and/or site notifications will be issued by the sponsor. Discrepancy resolution will be documented within the database audit trail.

Nerivio TCH-004 Clinical Study Protocol (NCT04089761)

Doc ID: TEC0105

Revision #: 1.0
Page: 39 of 49

8.3. Electronic signatures

The PI will electronically sign each individual eCRF after the data has been cleaned, monitored and reviewed. The electronic signature asserts that the investigator reviewed the eCRFs, the data queries, and the site notifications, and agrees with the content. Any changes made to the data after an electronic signature has been applied will result in invalidation of the original signature, and the PI will be required to re-sign the data after reviewing the change(s).

8.4. Verification, validation and securing of electronic data capture system

Verification and validation of the EDC and eCRFs will be performed by a team comprising representatives of the developer, the sponsor and at least one of the participating sites. A verification and validation report will be detained by the sponsor.

8.5. Records and data retention

A copy of all records (e.g., informed consent documents, source data, safety reports, study device dispensing records, etc.) which support case report forms for this study, will be retained in the files of the responsible investigator for a minimum of five (5) years following notification by the sponsor that all investigations (not merely the investigator's portion) are completed, terminated and/or discontinued. If the principal investigator retires, relocates, or for other reasons withdraws from the responsibility of keeping the study records, custody must be transferred to a person who will accept the responsibility. The sponsor must be notified in writing of the name and address of the new custodian within 5 days after such transfer occurs.

The database will be retained by the EDC system provider for a minimum of 5 years.

8.6. Other aspects of clinical quality assurance

The site PI or a person designated by the site PI is responsible for establishing and maintaining compliance with the study protocol. The study PI is responsible for addressing quality assurance issues (e.g. correcting procedures that are not in compliance with the protocol). The study coordinator is responsible for quality control issues (e.g. correcting errors in data entry). The sponsor will monitor the investigational sites throughout the study. All outstanding issues and findings that site personnel become aware of will be communicated and handled in agreement with a monitoring plan. An independent DMC will be responsible for providing oversight of the data monitoring issues and conducting periodical reviews that may include recommendations regarding enrollment, continuation, modification, or termination of the study.

Nerivio TCH-004 Clinical Study Protocol (NCT04089761)

Doc ID: TEC0105

Revision #: 1.0

Page: 40 of 49

Site audits by the sponsor may be conducted before the completion of the study to ascertain data quality and integrity.

The Food and Drug Administration (FDA) and/or the local state health authorities may request access to all study records, including source documents, for inspection. The investigator and site staff agree to cooperate with these audits. The investigator must notify the sponsor of any health authority audit as soon as notification of such audit is made. A representative or designee of sponsor may be present during a health authority audit.

9. Amendments and deviations from the protocol

9.1. Protocol amendments

The protocol cannot be amended by the investigator without obtaining the sponsor's approval. Protocol amendments will be submitted for approval to local IRB/EC and, if applicable, to the respective regulatory authority (RA). The amendments can be implemented in the study only after an IRB/EC and/or RA approval are obtained. Non-substantial changes (e.g. minor logistical or administrative changes, change of monitor(s), telephone numbers, renewal of insurance) which do not affect the rights, safety and well-being of human subjects and/or are not related to the clinical investigation objectives or endpoints, may only require a notification to the IRB/EC and/or regulatory without protocol amendment.

The following documents are relevant to the protocol but are not considered part of the protocol. These documents are stored and modified separately. As such, modifications to these documents do not require protocol amendments:

- Site roster
- Case report forms
- Data management plan
- Monitoring plan
- Statistical analysis plan
- DMC

9.2. Protocol deviations

A protocol deviation is any noncompliance with the clinical study protocol, Good Clinical Practice, or related SOPs requirements. The deviation may be associated with the subject, the investigator, or study personnel. The investigator/co-investigators must obtain the sponsor's approval for all protocol deviations, except for cases in which the safety and well-being of a patient will be affected, as stated in section 4.5.4 b of the ISO 14155 (2011).

Nerivio TCH-004 Clinical Study Protocol (NCT04089761)

Doc ID: TEC0105

Revision #: 1.0

Page: 41 of 49

Compliance with the protocol will be assessed by the study monitor during the monitoring visits as well as remotely, using designated reports provided by the EDC system. All protocol deviations will be addressed in study subject source documents and promptly reported to the site IRB, according to local requirements.

9.3. Procedures for recording, reporting and analyzing protocol deviations

All protocol deviations will be documented in source documents and appropriate eCRFs.

The study monitor is responsible for identifying and reviewing protocol deviations with the investigator or designee and documenting the issue and action/outcome of the protocol deviation in the MVR and any follow up letter/communication with the principal investigator.

The study monitor will ensure that major protocol deviations are discussed with the investigator. Major deviations include deviations that:

- impact patient safety
- alter the risk/benefit ratio
- compromise the integrity of the data
- affect willingness of the patient's participation in the study

The deviations will be reported to the IRB/EC periodically or as specified by the local regulations. Further documentation of any changes in research activity should be submitted to the sponsor and the IRB/EC if the deviations are related to any instance of serious or continuing non-compliance with governing regulations/requirements of the IRB/EC, and/or related to changes in protocol specified patient activity and procedures.

In addition to the immediate reporting, the study monitor will document all deviations in the monitoring visit report and follow-up letters. The monitor will discuss deviations with relevant site personnel. If needed, a note to file will be issued and filed in the relevant file and a copy will be sent to the sponsor. The sponsor or its designee will review records of deviations and will consider the need for corrective and preventive action and further external reporting to regulatory authorities. Deviations will be summarized and included in the study report. The potential impact/lack of impact of the deviations on the study results will be assessed.

9.4. Notification requirement and timelines

Major deviations should be escalated to the sponsor within 5 business days. Protocol deviations must be reported to local IRB/EC according to their guidelines. The site PI or other designated site staff member is responsible for adhering to local IRB/EC requirements.

Nerivio TCH-004 Clinical Study Protocol (NCT04089761)

Doc ID: TEC0105

Revision #: 1.0

Page: 42 of 49

10. Device accountability

The devices will be provided by Theranica Bioelectronics (sponsor), with all required labeling. The device number will be documented in the CRF and in the site log when provided to the participant. Each batch of devices delivered to the clinical sites for allocation to study participants will be accompanied with a shipment note. The device shipment records will be maintained by the sponsor as well as on site.

Prior to distribution, the devices will be stored in a designated locked cabinet. The access to the investigational devices will be controlled by the research staff. The devices will only be used in the clinical investigation and according to the study protocol.

Each device has a sticker on it with a unique number. When a device will be provided to the participant, it will be paired with the participant's smartphone using Bluetooth connection. During device allocation, application installation and device—smartphone pairing, a site allocated user ID will be entered by the study coordinator via the application. The three IDs (user ID, phone ID, device ID) provide a mean for identifying technical and PRO data from each participant in the electronic database while protecting participant's privacy.

The investigators will be responsible for the safe storage of the devices according to the instructions provided by Theranica Bioelectronics, with restricted access to the investigational materials in their possession, thereby preventing use of any materials by any person not participating in the study. The device accountability records will be reviewed during the monitoring visits.

The investigator will be responsible for providing device use training to the participants according to the instructions for use and protocol and for maintaining product inventory and records. As part of study closure, all unused devices must be returned in their original packaging to Theranica Bio-Electronics.

11. Informed consent process

Informed consent and assent must be obtained from the parent/caregiver and participant, respectively, before any protocol-related activities are performed. Participants must be provided with a signed copy of the consent and assent forms. The eCRFs will be updated that informed consent and assent have been signed.

12. Adverse events

Adverse event (AE) is defined as any unfavorable and unintended medical change, temporally associated with the use of the sponsor's product, whether or not considered related to the use of the product. Any worsening (i.e., any clinically significant adverse

Nerivio TCH-004 Clinical Study Protocol (NCT04089761)

Doc ID: TEC0105

Revision #: 1.0

Page: 43 of 49

change in frequency and/or intensity) of a preexisting condition which is temporally associated with the use of the sponsor's product, is also an adverse experience. An adverse device effect (ADE) is an adverse event related to the use of the investigational device. In this study the ADE refers to side effect and complications.

A serious adverse event (SAE) is defined as an adverse event that leads to a) death,

- b) serious deterioration in the health of the subject, that either resulted in
 - 1) a life-threatening illness or injury, or
 - 2) a permanent impairment of a body structure or a body function, or
 - 3) in-patient or prolonged hospitalization, or
 - 4) medical or surgical intervention to prevent life-threatening illness or injury or permanent impairment to body structure or body function
- c) fetal distress, fetal death or a congenital abnormality or birth defect

A serious device related adverse effect (SADE) is an adverse event related to the use of the investigational device and that is considered by regulations and definitions as serious.

12.1. Characteristics of AEs

An investigator who is a qualified physician, will evaluate all adverse events as to:

Maximum intensity

Mild: awareness of symptom, but easily tolerated Moderate: definitely acting like something is wrong

Severe: extremely distressed or unable to do usual activities

Duration

Record the start and stop dates of the adverse experience. If less than 1 day, indicate the appropriate length of time and units

Relationship of an AE and SAE to the study device

The relationship of the adverse event to the study device is defined as:

Definitely related: There is evidence of exposure to the device. The temporal sequence of the AE onset relative to use of the device is reasonable. The AE is more likely explained by the device than by another cause. Dechallenge is positive. Rechallenge (if feasible) is positive. The AE shows a pattern consistent with previous knowledge of the device.

Probably related: There is evidence of exposure to the device. The temporal sequence of the AE onset relative to use of the device is reasonable. The AE is more likely explained by the device than by another cause. Dechallenge (if performed) is positive.

Nerivio TCH-004 Clinical Study Protocol (NCT04089761)

Doc ID: TEC0105

Revision #: 1.0 Page: 44 of 49

Possibly related: There is evidence of exposure to the device. The temporal sequence of the AE onset relative to use of the device is reasonable. The AE could have been due to another equally or less likely cause. Dechallenge (if performed) is positive.

Definitely not related: The subject/patient did not use the device; or temporal sequence of the AE onset relative to device use is not reasonable; or there is another obvious cause of the AE.

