6.4. Study endpoints

6.4.1. Primary endpoints

1. The safety of Nerivio

The incidence of adverse events in general and by seriousness, severity and association to the device.

2. Treatment tolerability

The percent of subjects who fail to complete the study because of adverse events

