7.2. Endpoints

7.2.1. Primary endpoints

The primary endpoints of the study are related to the safety of the device. Safety and tolerability will be assessed by review of all safety parameters, including adverse events. The incidence of adverse events will be assessed as a function of severity and association to the device. The time of resolution of the adverse events and need for treatment will also be analyzed.

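### The causality scale in 12.1 has no category for an event with a more likely but not obvious other cause, or for a negative dechallenge without an obvious cause, so the device-association part of primary endpoint 1 depends on the rater

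*Combined protocol and SAP*

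**What the plan says.** Primary endpoint 1 (6.4.1) is "The incidence of adverse events in general and by seriousness, severity and association to the device". Section 7.2.1 repeats the link: "The incidence of adverse events will be assessed as a function of severity and association to the device". Section 7.5.3 adds that device-related events, serious and otherwise, will be documented.

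The rating comes from 12.1, where a physician investigator places each event in one of four categories:

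- **Definitely related:** exposure, reasonable timing, device the more likely explanation, positive dechallenge, positive rechallenge where feasible, and a pattern that matches what is known of the device.
- **Probably related:** exposure, reasonable timing, and "The AE is more likely explained by the device than by another cause". On dechallenge: "Dechallenge (if performed) is positive".
- **Possibly related:** the same exposure, timing and dechallenge conditions, but "The AE could have been due to another equally or less likely cause".
- **Definitely not related:** the device was not used, or "temporal sequence of the AE onset relative to device use is not reasonable; or there is another obvious cause of the AE".

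There is no 'unlikely' category. Section 12.3 separately lists migraine symptoms, dizziness among them, that are never counted as device related.

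**The concern.** A causality scale should give every event exactly one place. Here the likelihood sentence is all that separates 'Probably' from 'Possibly', and it appears to point the wrong way. 'Possibly' takes in alternatives less likely than the device, which 'Probably' already covers. It leaves out alternatives more likely than the device, which only 'Definitely not' could otherwise take, and then only if they are obvious.

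What is at stake is the reproducibility of the device-related count. The trial is single-arm, open-label and multicentre, so there is no control arm in which inconsistent attribution would show. The goal in 5.1 is headache relief without unexpected device-related effects. The extra monitoring of events still ongoing at the last visit (12.2) also depends on whether they were rated device related.

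**Working it through.** The plan gives no figure here to reproduce. The check is one of logic, followed by a small calculation for scale.

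**Step 1. Which categories apply.** Take a participant who used the device and had an event with reasonable timing, no obvious other cause, and no place on the 12.3 list. Vary the likelihood of the other cause and the dechallenge result, and apply 12.1 literally:

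| Other cause, relative to device | Dechallenge positive | Not done | Negative |
|---|---|---|---|
| Less likely | Probably and Possibly (Definitely too, if its extra criteria are met) | Probably and Possibly | none |
| Equally likely | Possibly | Possibly | none |
| More likely | none | none | none |

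Five of the nine cells have no category, two have exactly one, and two have more than one. These are counts of combinations, not of expected events.

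- *Bottom row.* 'Definitely' and 'Probably' fail because the device is not the more likely explanation. 'Possibly' fails because the other cause is neither equally nor less likely. 'Definitely not' fails because the device was used, the timing is reasonable and the cause is not obvious. Arm ache with a plausible competing cause is an example.
- *Right-hand column.* All three related categories require a positive dechallenge when one is performed, and 'Definitely not' is closed as before. Arm pain that persists after stimulation ends could fall here.
- *Top row, first two cells.* A less likely other cause makes the device the more likely explanation, so 'Probably' and 'Possibly' are both met.

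If the other cause is obvious, 'Definitely not' is always met. A related category is met as well when that cause is no more likely than the device and dechallenge is not negative.

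**Step 2. Is it repaired elsewhere?** Section 12.1 has no tie-break or adjudication rule. Sections 6.4.1, 7.2.1 and 7.5.3 do not say which categories count as device-related. Section 12 defines an adverse device effect only as an event related to use of the device. The data monitoring committee in 6.7 reviews device-related events but is not asked to classify them. The 12.3 list settles common migraine symptoms and nothing else.

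**Step 3. Scale.** Inputs: 110 participants, up to 130 (7.3); adult active-arm device-related incidence 6/126 = 4.8% (4.2.2, Table 5). Assumptions: the adult rate carries over, and the safety set has 110 or 130 participants.

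- One participant moved: 1/110 = 0.9 points; 1/130 = 0.8 points.
- Expected count: 110 × 6/126 = 5.2, about 5; 130 × 6/126 = 6.2, about 6.
- Exact (Clopper–Pearson) 95% limits for x of n: lower = 2.5% quantile of Beta(x, n−x+1); upper = 97.5% quantile of Beta(x+1, n−x).

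| n | Expected count | With three more rated related (illustration) |
|---|---|---|
| 110 | 5: 4.5% (1.5 to 10.3) | 8: 7.3% (3.2 to 13.8) |
| 130 | 6: 4.6% (1.7 to 9.8) | 9: 6.9% (3.2 to 12.7) |

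The three extra participants are arbitrary. The documents do not say how many events would fall in the gap.

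**Step 4. Does rewording close it?** If 'Possibly' covers an equally or more likely, but not obvious, other cause, the first two cells of the bottom row become 'Possibly' and the overlap in the top row disappears. The right-hand column stays empty, so negative dechallenge needs its own rule.

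**The case against.** The strongest reply has four parts.

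1. *The overlap resolves itself.* The scale is already nested, since every 'Definitely' event meets the criteria for 'Probably'. Such scales are read by taking the highest category met. On that reading the Probably/Possibly overlap goes away, and it never alters a total that pools the three related categories. This largely stands. The rule is not written down, however, and it does nothing for events that meet no category.

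2. *The 12.3 list removes many doubtful events.* This is true. Dizziness, for instance, is not a gap event, because the protocol already rules it not device related. Events off the list are still exposed.

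3. *The consequences are limited.* The primary endpoints are descriptive, with no threshold or test. Overall incidence, seriousness, severity and withdrawal because of adverse events do not depend on this wording, and serious events go to the sponsor within 1 business day whatever their cause. All of this stands, and it confines the point to the device-association breakdown.

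4. *Raters will treat 'Possibly' as the residual class.* Many may do so, but the text restricts that class to equally or less likely alternatives. A rater who follows it literally could as well choose 'Definitely not'.

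A reader might also infer a range from the adult data: 19/126 had any adverse event, 110 × 19/126 = 16.6, about 17, so device-related incidence could run from 4.5% up to 17/110 = 15.5%. The documents do not support this. The upper end needs every other participant with an event to have one that falls in the gap, lies off the 12.3 list and is rated 'Possibly'. The lower end is not a floor, because gap events can also be under-counted, and nothing says that the adult trial used this scale. Nor does any figure show that the gap case is the commonest kind of doubtful event.

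**Conclusion.** The point holds as a fault in a stated rule, and nothing elsewhere in the documents corrects it. Two kinds of event have no category: those with a more likely but not obvious other cause, and those with a negative dechallenge and no obvious cause. Forcing them into 'Possibly' or 'Definitely not' makes the device-association part of primary endpoint 1 rater-dependent, in either direction. That conclusion assumes that 'Possibly' counts as device-related, which the plan does not state.

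The total effect cannot be computed. What can be said is the shift per reclassified participant, 0.9 points at n=110 or 0.8 at n=130, which is not negligible beside an adult rate of 4.8%. The overlap with 'Probably' is secondary: it blurs the breakdown by degree, and reaches the total only if 'Possibly' is excluded. A reader might go further and conclude that the primary safety result as a whole is unreliable. The documents do not support that, since the other components of the primary endpoints are unaffected.

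**What to change.** In 12.1 and on the adverse event form:

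- Reword the likelihood condition of 'Possibly related' to another equally or more likely, but not obvious, cause.
- Assign events with a negative dechallenge and no obvious other cause to a named category.
- State that the highest category met applies.

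In 6.4.1, 7.2.1 and 7.5.3, define device-related incidence as Definitely + Probably + Possibly, and show each category separately as well. Pooling all three is a cautious convention, not a logical necessity; the separate display lets a reader draw the line elsewhere.

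The cost is a few phrases in the protocol and on the form, with no new data collection. The downside is that reported device-related incidence may be somewhat higher, because events with a more likely but not obvious other cause would count as 'Possibly related'.
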